1.8 Specimen Collection

Primary Specimen Collection

The research samples collected will be studied using standard laboratory assays for:

1. SARs-CoV-2 RNA

Types of Specimens:

- Saliva, oral, nasal, and pharyngeal swabs, and sputum (if spontaneously producing sputum or intubated) for SARS-CoV-2 RNA will be collected at baseline day 0, day 7 and day 14 in a subset of patients.
- Urine samples will be collected on day 1 and day 14.
- Annotation: Data to be annotated or associated with each specimen include participant ID (PID), date and time of collection, and specimen type. A PID will be assigned at the time of screening; at the time of specimen collection, all specimens collected will be labelled with the PID, date/time of collection, study timepoint, and specimen type. No identifiers will be included on the labels. These PIDs will be used to link the specimens with REDCap database containing the data collected from the EHR. All identifiers include name and date of birth matched to PID will be kept in a separate encrypted, password-protected electronic file that is accessible only by designated study personnel.
- Transport: All samples will be collected into sealed container(s) with de-identified PIDencoded labels and placed in a cooler. Samples will be transported to the hospital hematology and microbiology labs by trained personnel. The respiratory samples (saliva, swabs, sputum) will be processed in the [name] laboratory. Urine specimens will be transported by the study coordinator to a -80C freezer in the MSB A900 unit for temporary storage until analysis.
- Processing: Specimen processing will occur in accordance with approved Rutgers NJMS Institutional Biosafety Committee protocols.
- Storage: Urine will be stored at -80C in freezers in the MSB until processing and accessible by the study investigators and their laboratory personnel. Respiratory samples will be stored at -80C in the RBL, accessible by [name] and their laboratory personnel.
- Disposition: Analysis will occur at the end of the study/accrual period. Any unused specimens will be discarded upon study completion following appropriate biohazard disposal procedures by [name] laboratory personnel for the respective specimens.

B. Secondary Specimen Collection

N/A

Protocol Title: ATTAC-19 - Aggrenox To Treat Acute Covid-19 Pro#2020001469

Protocol Version 6 Date: 4/18/2021

7/21/2021

Rutgers, The State University of New Jersey [name]

1.9 Data Collection

1. Primary Data Collection

Electronic COVID case report forms (eCRFs)²⁴ have been designed to collect the data points outlined in section 1.3 (D). Completion of the electronic CRFs (eCRFs) will be done in accordance with the instructions in a study specific data capture plan. All eCRFs will be completed by the research staff of the Clinical research unit. The eCRFs will be maintained in a confidential format in the RedCap database.

2. Secondary Data Collection N/A

1.10 Timetable/Schedule of Events

Please refer to Appendix A. All study procedures will be performed according to the schedule outlined in the Study Flow Table

2.0 Project Management

2.1 Research Staff and Qualifications

Researchers and research Staff are part of the Rutgers- New Jersey Medical School, and/or Clinical Research Unit (CRU) Rutgers University. The Investigators and staff are qualified by training and experience for their research roles, including knowledge of applicable laws, regulations, codes, guidance, and relevant professional standards.

2.2 Research Staff Training

All research team members will complete the required Human Subject Protection training through the Collaborative Institutional Training Initiative (CITI) Program prior to being approved to take part on this study. All study members will attend the site initiation visit for training about the study specific protocol.

The Principal Investigator will provide oversight and ensure that the study is conducted according to the investigational plan and applicable regulations in accordance with 21 CFR 312.

2.3 Resources Available

Aggrenox Capsule (25 mg aspirin/200 mg extended-release dipyridamole) will be provided at no charge to the study participants.

3.0 Multi-Center Research

NA

4.0 Subject Considerations

4.1 Subject Selection and Enrollment Considerations

1. Method to Identify Potential Subjects

An IRB approved press release will be distributed to Rutgers physicians through the Rutgers Communications Office. Press release will have a phone number for the Rutgers physicians to call the research team about the hospitalized patient as a potential study participant. Potential study participants will also be identified by the research team members. Screening will be conducted by to be named Advanced Practice Nurse and Research Nurse. All research personnel will wear appropriate PPE as outlined.

2. Recruitment Details

The subjects will be adults age 18 years and older with a diagnosis of COVID-19 and a confirmed positive test for SARS-CoV-2 by any accepted method. Potential study participants will be recruited by the research team members. The research team will also review each page of the informed consent document with the patient or authorized proxy. This study will be available to all patients who meet the eligibility criteria. There will be no limitation to access with regards to race or gender. Patients will be required to sign/ verbal consent on an IRB- approved informed consent form prior to commencing any research related activity.

Subject Screening

If the patient lacks decision-making capacity, then authorized proxy will be approached for the consent for the patient to participate in this study. The treating investigator and research team will interview the patient/ proxy and review the chart to determine if the patient is a potential candidate for the study. Screening tests to confirm whether subjects are eligible for inclusion in this study will be conducted including SARS-CoV-2 test if not already confirmed to be positive. The Principal Investigator, or designee, will be responsible for reviewing and confirming subject eligibility prior to enrollment to the study.

Subjects who do not meet all inclusion criteria will be recorded as screen failures in RedCap.

Inclusion Criteria:

1. Age ≥18 years.

Protocol Title: ATTAC-19 – Aggrenox To Treat Acute Covid-19 Pro#2020001469

Protocol Version 6 Date: 4/18/2021

IRB ID: Pro2020001469
Approval Date: 5/25/2021
Expiration Date: 7/21/2021

Rutgers, The State University of New Jersey [name]

- 2. Hospitalization.
- 3. SARS-CoV-2 viral nucleic acid positive within 3 days.
- 4. Lab test result pending plus a high clinical suspicion for SARS-CoV-2 (fever and cough for ≤ 7 days, bilateral pulmonary infiltrates on imaging or new hypoxemia with spO2 ≤94% on room air or no alternative explanation for respiratory symptoms).
- 5. Willing and able to provide consent or by authorized proxy.

Exclusion Criteria:

- 1. Pregnancy.
- 2. History of G-6PD deficiency.
- 3. Use of antiplatelet agents including inhibitor of P2Y12 ADP platelet receptors, phosphodiesterase inhibitors, and Glycoprotein IIB/IIIA inhibitors.
- 4. On therapeutic anticoagulation with coumadin, unfractionated heparin, enoxaparin (lovenox) and direct oral anticoagulants. (prophylactic anticoagulation is now standard of care and patients on prophylactic anticoagulation such as enoxaparin or unfractionated heparin, will be included in the study)
- 5. Vasodilatory shock.
- 6. Patient with known ongoing angina, recent myocardial infarction and sub-valvular aortic stenosis.
- 7. Active gastric or duodenal ulcer or any bleeding disorder or creatinine clearance < 10.
- 8. Hemoglobin <9 mg/dL, platelet count of <30,000 /mm³.
- 9. Acute respiratory infection for >10 days.
- 10. Known allergy/hypersensitivity to Dipyridamole and/or Aspirin.
- 11. Severe hepatic or renal insufficiency.
- 12. Uncontrolled hypertension defined as systolic > 180 mm Hg or diastolic > 100 mm Hg.
- 13. Patients with known allergy to NSAIDs
- 14. Patients enrolled in other non-standard of care clinical trials.

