- o Medical history
- o Physical examination will be performed as part of the routine care and will be abstracted from the medical record
- o Vital signs (blood pressure, heart rate, temperature) will be abstracted from the medical record
- o Electrocardiogram will be performed as part of the routine care and will be abstracted from the medical record
- o Labs: CBC, BMP, Coagulation profile, Ferritin, D-Dimer, CRP. will be collected as part of the routine care and will be abstracted from the medical record
- o Concomitant medications (starting from the time the patient signs the informed consent)
- o Collection of research samples:
 - Saliva, oral, nasal, and pharyngeal swabs, and sputum (if spontaneously producing sputum or intubated) for SARS-CoV-2 RNA will be collected at baseline day 0
- Randomize study participant through RedCap.

Treatment Period –Days 1 - 14 (Complete daily COVID Case report form – Appendix B: Module 2)

- Clinical assessment completed by Research Nurse. May be conducted by phone if the patient is discharged before 14 days.
 - Review of daily temperatures
 - Review of medication compliance
 - Adverse events

Protocol Title: ATTAC-19 – Aggrenox To Treat Acute Covid-19 Pro#2020001469

Rutgers, The State University of New Jersey [name]

- Record standard of care treatments and/or procedures prescribed
- Labs: At day 7 and day 14: we will abstract CBC, BMP, Coagulation profile, Ferritin, D-Dimer, CRP results from the medical record.

Collect research specimens:

- Saliva, oral, nasal, and pharyngeal swabs, and sputum (if spontaneously producing sputum or intubated) for SARS-CoV-2 RNA will be collected at day 7 and day 14 in a subset of patients.
- Urine samples will be collected on day 1 and day 14.

Treatment Period –Days 15 - 28 (Complete daily COVID Case report form – Appendix B: Module 2)

- Clinical assessment completed by Research Nurse. May be conducted by phone if the patient is discharged before 14 days.
 - Review of daily temperatures
 - Adverse events
 - Record standard of care treatments and/or procedures prescribed
 - COVID ordinal outcomes scale on day 28.

Discharge/ Death: Complete COVID Case report form –(Appendix B: Module 3)

Treatment Plan:

Participants will be randomized 1:1 to Aggrenox or standard treatment.

- Active Comparator: (Aggrenox (Dipyridamole ER 200mg/ Aspirin 25mg orally/enterally).

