 Participants will receive Aggrenox (Dipyridamole ER 200mg/ Aspirin 25mg orally/enterally), 2 times daily (FDA–recommended dose) starting on the day of enrollment for a total of 2 weeks + standard care.
- Standard care Comparator: Participants will receive standard care starting on the day of enrollment for a total of 2 weeks.

2. Subject Enrollment

- 1. Patients who are eligible for the study will be enrolled in the clinical trial after they or their authorized proxy provide informed consent for study participation. A copy of the institution's IRB approved informed consent will be on file RedCap. The patients will be enrolled through RedCap, the Clinical Trials Management System for this study. Contact the Rutgers Clinical Trials Unit, if you have any questions about the Registration/Enrollment process.
- Registration: Any subject that has signed the consent will be entered into RedCap. A Copy of the consent will be uploaded into the Documents section.
- Enrollment: Once eligibility has been confirmed, the completed, signed and dated eligibility checklist will be uploaded into the Documents section. RedCap will randomize the patient and a sequence number (subject study ID) will be generated at the time of enrollment, this is the point the patient is considered on study.

Protocol Title: ATTAC-19 – Aggrenox To Treat Acute Covid-19 Pro#2020001469

Rutgers, The State University of New Jersey [name]

Patients will not start protocol treatment prior to registration.

3. Study Safety Assessments

The Principal Investigator is responsible for ensuring that all staff involved in the study are familiar with the content of this section.

Definitions:

Adverse Events:

An adverse event is the development of an undesirable medical condition or the deterioration of a pre-existing medical condition following or during exposure to a pharmaceutical product, whether considered causally related to the product. An undesirable medical condition can be symptoms (e.g. nausea, chest pain), signs (e.g. tachycardia, enlarged liver) or the abnormal results of an investigation (e.g. laboratory findings, electrocardiogram). In clinical studies, an AE can include an undesirable medical condition occurring at any time, including run-in or washout periods, even if no study treatment has been administered. The term AE is used to include both serious and non- serious AEs.

Serious Adverse Events:

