1.7 Drugs/Devices/Biologics

Generic name: Dipyridamole and Aspirin

Commercial name: Aggrenox

[figure not shown]
Aggrenox is a combination antiplatelet agent intended for oral administration. Each hard gelatin capsule contains 200 mg dipyridamole in an extended-release form and 25 mg aspirin, as an immediate- release sugar-coated tablet. In addition, each capsule contains the following inactive ingredients: acacia, aluminum stearate, colloidal silicon dioxide, corn starch, dimethicone, hypromellose, hypromellose phthalate, lactose monohydrate, methacrylic acid copolymer, microcrystalline cellulose, povidone, stearic acid, sucrose, talc, tartaric acid, titanium dioxide, and triacetin. Each capsule shell contains gelatin, red iron oxide and yellow iron oxide, titanium dioxide, and water.

Source: Commercially available

For complete information please refer to the package inserts at https://dailymed.nlm.nih.gov/dailymed/search.cfm?labeltype=all&query=aggrenox

Dipyridamole

Dipyridamole is an antiplatelet agent chemically described as 2,2',2",2"'-[(4,8-Dipiperidinopyrimido[5,4-d]pyrimidine-2,6-diyl)dinitrilo]-tetraethanol. It has the following structural formula:

C₂₄H₄₀N₈O₄ Mol. Wt. 504.63

Dipyridamole is an odorless yellow crystalline substance, having a bitter taste. It is soluble in dilute acids, methanol and chloroform, and is practically insoluble in water.

Aspirir

The antiplatelet agent aspirin (acetylsalicylic acid) is chemically known as benzoic acid, 2-(acetyloxy)-, and has the following structural formula: CgHgO4 Mol. Wt. 180.16

Protocol Title: ATTAC-19 – Aggrenox To Treat Acute Covid-19

Pro#2020001469

Protocol Version 6 Date: 4/18/2021

7/21/2021

Approval Date: Expiration Date:

Aspirin is an odorless white needle-like crystalline or powdery substance. When exposed to moisture, aspirin hydrolyzes into salicylic and acetic acids, and gives off a vinegary odor. It is highly lipid soluble and slightly soluble in water.

[figure not shown]
12 CLINICAL PHARMACOLOGY 12.1 Mechanism of Action

The antithrombotic action of AGGRENOX is the result of the additive antiplatelet effects of dipyridamole and aspirin.

Dipyridamole

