4.7 Risks of Harm/Potential for Benefits to Subjects

A. Description of Risks of Harm to Subjects

Reasonably Foreseeable Risks of Harm (this data I got from Aggrenox product information available online- Appendix is attached for your review))

Risk of Bleeding

AGGRENOX increases the risk of bleeding.

Risk factors for bleeding include the use of other drugs that increase the risk of bleeding (e.g., anticoagulants, antiplatelet agents, heparin, anagrelide, fibrinolytic therapy, and chronic use of NSAIDs).

Intracranial Hemorrhage In European Stroke Prevention Study-2 (ESPS2), the annualized event rate for intracranial hemorrhage was 0.39%/year in the AGGRENOX group, 0.26%/year in the extended-release dipyridamole (ER-DP) group, 0.24%/year in the aspirin (ASA) group, and 0.29%/year in the placebo groups.

Gastrointestinal (GI) Side Effects

GI side effects include stomach pain, heartburn, nausea, vomiting, and gross GI bleeding. Although minor upper GI symptoms, such as dyspepsia, are common and can occur anytime during therapy, physicians should remain alert for signs of ulceration and bleeding, even in the absence of previous GI symptoms. Inform patients about the signs and symptoms of GI side effects and what steps to take if they occur. In ESPS2, the annualized event rate for gastrointestinal bleeding was 2.97%/year in the AGGRENOX group, 1.58%/year in the extended-release dipyridamole group, 2.06%/year in the aspirin group, and 1.40%/year in the placebo groups.

Peptic Ulcer Disease

Avoid using aspirin in patients with a history of active peptic ulcer disease, which can cause gastric mucosal irritation and bleeding.

Alcohol Warning

Because AGGRENOX contains aspirin, counsel patients who consume three or more alcoholic drinks every day about the bleeding risks involved with chronic, heavy alcohol use while taking aspirin.

Renal Failure

Avoid aspirin in patients with severe renal failure (glomerular filtration rate less than 10 mL/minute) [see Use in Specific Populations.

Hepatic Insufficiency

Elevations of hepatic enzymes and hepatic failure have been reported in association with dipyridamole administration.

Coronary Artery Disease

Protocol Title: ATTAC-19 – Aggrenox To Treat Acute Covid-19

Pro#2020001469

Protocol Version 6 Date: 4/18/2021

7/21/2021

Rutgers, The State University of New Jersey [name]

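### The hemoglobin limit in exclusion criterion 8 carries a unit that makes it impossible to meet, so read literally it excludes nobody on hemoglobin

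*Combined protocol and SAP*

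**What the plan says.** The exclusion list in Section 4.1 (Subject Selection and Enrollment Considerations) opens criterion 8 with "Hemoglobin <9 mg/dL, platelet count of" and closes it with a platelet value of less than 30,000/mm³. The two limits are separated by a comma with no conjunction. It is the only place in the protocol text where a hemoglobin value appears.

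The surrounding text that bears on it:

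- Section 1.7 describes the study drug: "Aggrenox is a combination antiplatelet agent intended for oral administration".
- Section 4.7, under bleeding risk: "AGGRENOX increases the risk of bleeding". Heparin and other anticoagulants are listed there among the risk factors.
- Criterion 4 excludes therapeutic anticoagulation but states that "patients on prophylactic anticoagulation such as enoxaparin or unfractionated heparin, will be included in the study".
- Criterion 7 excludes "Active gastric or duodenal ulcer or any bleeding disorder or creatinine clearance < 10". Criterion 3 excludes use of other antiplatelet agents, and criterion 11 severe hepatic or renal insufficiency.
- The Day 0 screening list in Research Design and Methods says "Labs: CBC, BMP, Coagulation profile, Ferritin, D-Dimer, CRP. will be collected as part of the routine care". The blood count is the source of the hemoglobin value, and no unit is given.
- Under Subject Enrollment in the same section, once eligibility is confirmed "the completed, signed and dated eligibility checklist will be uploaded into the Documents section", and RedCap then randomizes the patient. The checklist itself is not reproduced.

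**The concern.** Criterion 8 is a decision rule, not background text. Someone compares a laboratory value with a printed number and the patient is randomized or not. A printed number that no value can fall below means that half of the rule does nothing.

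The context makes this more than cosmetic. The drug is an antiplatelet that the protocol says raises bleeding risk, and patients on prophylactic heparin or enoxaparin are deliberately included. A hemoglobin floor presumably serves to keep out patients with little reserve if they bleed. That purpose is an inference from the stated risks; the protocol does not give a reason for the criterion.

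What is at stake is consistent application. A screener who follows the text never excludes on hemoglobin. A screener who mentally corrects the unit applies a limit that the protocol does not contain. The audits and deviation reviews described in Section 6.3 would then be comparing practice with a printed rule that differs from the one in use.

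**Working it through.** **Inputs.** Printed limit: 9 mg/dL (Section 4.1, criterion 8). Conversion: 1 g/dL = 1,000 mg/dL = 10 g/L. The documents give no range of patient hemoglobin, so I assume 1 to 15 g/dL, with 1 g/dL as a deliberate extreme. The protocol gives no derivation of the limit, so there is no calculation to reproduce.

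**Step 1: convert the limit.**

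9 mg/dL ÷ 1,000 = 0.009 g/dL, and 0.009 g/dL × 10 = 0.09 g/L.

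**Step 2: compare it with hemoglobin values.**

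| Hemoglobin (g/dL) | In mg/dL | Multiple of the printed limit | Below 9 mg/dL? |
|---|---|---|---|
| 1 | 1,000 | 1,000 ÷ 9 ≈ 111 | No |
| 3 | 3,000 | 3,000 ÷ 9 ≈ 333 | No |
| 5 | 5,000 | 5,000 ÷ 9 ≈ 556 | No |
| 7 | 7,000 | 7,000 ÷ 9 ≈ 778 | No |
| 15 | 15,000 | 15,000 ÷ 9 ≈ 1,667 | No |

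The answer is the same across the whole assumed range, so it does not depend on the range chosen. For scale only, the same numeral in g/dL would be a limit 1,000 times higher. That shows the size of the unit error; it does not establish what limit was intended.

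**Step 3: what the comma does.** Let H be the statement that hemoglobin is below the printed limit, and P that platelets are below 30,000/mm³. From Step 2, H is always false.

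- Joined by 'or': (H or P) reduces to P. The platelet limit works and only the hemoglobin part is idle.
- Joined by 'and': (H and P) is always false. Criterion 8 excludes nobody, and the platelet limit is lost as well.

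**Step 4: what else could exclude these patients.** Criteria 3, 4, 7 and 11 act on antiplatelet use, therapeutic anticoagulation, ulcer or bleeding disorder or very low creatinine clearance, and severe hepatic or renal insufficiency. Some anaemic patients will be excluded on those grounds. None of the four sets a hemoglobin value, so none replaces the missing limit.

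**Step 5: design figures.** Hemoglobin is not an input to the sample-size statement in Section 1.5 (132 patients, mean 4.5, SD 1.6, 20% relative difference, 90% power) or to the analysis in Section 6.1. Nothing there changes.

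**The case against.** The strongest reply is that this is an obvious slip which nobody would apply literally. A limit that no patient can meet announces itself as a unit error to anyone reading a blood count. The trial has one site, the research team reviews the chart, and the principal investigator or a designee confirms eligibility before enrollment. Several other criteria already address bleeding risk. No misapplied screening decision is shown.

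Most of that stands, and it limits the point. A reader might infer that the trial admits every anaemic patient, or that it has no protection against bleeding. The documents support neither: only the hemoglobin part is certain to be inert, other criteria remain, and screeners at one site would probably notice. A reader might also infer that the signed checklist carries the same error. Its wording is not in the protocol, so that can only be checked. Nor do audits lack any limit. They have a printed one whose unit is implausible, and the protocol does not say how an auditor would treat it.

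What the reply does not do is supply the correct limit. No other part of the protocol text states one, and the screening list gives no unit. Recognising that a unit is wrong does not settle whether the number was meant to stand, and an eligibility threshold should not depend on each reader repairing it. The reply also leaves open whether the two limits are joined by 'and' or 'or'.

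**Conclusion.** The point holds in a limited form. The hemoglobin limit in criterion 8 is wrong as printed: at 0.009 g/dL it excludes no patient on hemoglobin. The platelet limit survives if the comma means 'or' and fails with it if the comma means 'and'. The consequence is a written eligibility threshold that may be applied unevenly. It is not a shown safety failure, and it has no bearing on sample size, power, endpoints or analysis.

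The conclusion rests on the unit conversion, on the assumption that every patient's hemoglobin is at least 1 g/dL (any value above 0.009 g/dL would do), and on the absence of another hemoglobin limit in the protocol text. That the unit is wrong follows from physical plausibility, not from a conflicting statement elsewhere. It is tempting to conclude that the intended rule is simply the same number in grams, but the documents do not say so and only the sponsor can confirm it. The share of patients whom the intended limit would exclude cannot be calculated from the documents.

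**What to change.** 1. The sponsor confirms the intended hemoglobin limit, both number and unit, and restates criterion 8 in the unit that the hospital laboratory reports.
2. The same edit replaces the comma with an explicit 'and' or 'or' between the hemoglobin and platelet limits, or splits them into two numbered criteria.
3. The study team checks whether the RedCap eligibility checklist repeats the printed limit, and aligns it if so.
4. Patients already enrolled are checked against the confirmed limit using the Day 0 blood count already abstracted from the record, and any discrepancies are documented.

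The cost is a short amendment, since Section 4.4 (Ongoing Consent) requires IRB approval before any protocol change takes effect, plus a checklist review and a look-up of existing laboratory values. No new procedure or data collection is needed.
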